1 SYNOPSIS

Name of Sponsor/Company: QED Therapeutics, Inc.	
Name of Investigational Product: Infigratinib (also known as BGJ398, BBP-831, and infigratinib phosphate; hereafter referred to as infigratinib)	
Name of Active Ingredient: Infigratinib	
Title of Study: Phase 3, Multicenter, Double-Blind, Randomized, Placebo-Controlled Trial of Infigratinib for the Adjuvant Treatment of Subjects with Invasive Urothelial Carcinoma with Susceptible FGFR3 Genetic Alterations (PROOF 302)	
Study centers: This is a multicenter study involving approximately 165 study centers worldwide.	
Medical Monitor: PPD	MD
Studied period (years): Estimated date first subject enrolled: December 2019 Estimated date last subject completed: 2024	Phase of development: 3
Objectives and Endpoints:	
Objectives	Endpoints
Primary: 
To determine if treatment with infigratinib improves centrally reviewed disease-free survival (DFS) compared with placebo treatment in subjects with invasive urothelial carcinoma with susceptible FGFR3 alterations after nephroureterectomy, distal ureterectomy, or cystectomy	
Centrally reviewed DFS, from date of randomization to local/regional or contralateral invasive or metastatic recurrence, or death due to any cause, whichever occurs earlier

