11.3.3 Efficacy Analyses

The primary objective of the study is to compare the centrally reviewed DFS of subjects with invasive urothelial cancer with susceptible FGFR3 alterations treated with infigratinib vs placebo following nephroureterectomy, distal ureterectomy, or cystectomy.

The primary endpoint is centrally reviewed DFS, from date of randomization to local/regional or contralateral invasive or metastatic recurrence (according to central review) or death due to any

cause, whichever occurs earlier. Criteria for recurrence are specified in Section 10.1. For subjects without a bladder who are alive and without recurrence (local/regional or contralateral invasive or metastatic) by BICR, DFS will be censored at the last radiology assessment. For subjects with a bladder who are alive and without recurrence, DFS will be censored at the last radiology assessment if the previous cystoscopy result within 6 months is negative for muscle invasive disease, otherwise DFS will be censored at the last complete recurrence assessment. Subjects who have no disease assessments after baseline or no death recorded will be censored on the randomization date.

Investigator-reviewed DFS including intraluminal low-risk (noninvasive, low-grade, or high-grade) recurrence is defined as the time from randomization to any recurrence as determined by the investigator, or death due to any cause, whichever occurs earlier. For subjects without documented recurrence and who are still alive, they will be censored at the last complete disease assessment (or, if no complete disease assessments are performed after the baseline visit or no death recorded, at the time of randomization day).

Investigator-reviewed MFS is defined as the time from randomization to any metastatic recurrence as determined by the investigator or death due to any cause, whichever occurs earlier. For subjects without documented metastatic recurrence and who are still alive, they will be censored at the last radiology assessment (or, if no radiology assessments are performed after the baseline visit or no death recorded, at the time of randomization day).

OS is defined as date of randomization to death. For subjects without documented death, they will be censored at the last known to be alive date.

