6 DEFINITIONS

Baseline

In general, the baseline value will be considered the last measurement observed prior to taking the first dose of study treatment. For ECG, if a set of triplet ECG are the last ECG collected prior to taking the first dose of study treatment, the average of the triplet ECG will be considered as baseline.

For subjects who are randomized and never receive study treatment, the baseline value will be the last assessment before randomization (on the day of or before randomization).

Investigational Product/Study Treatment

‘Investigational product’ or ‘study treatment’ is used to reference only infigratinib or placebo.

Long-term Follow-up Phase

The long-term follow-up phase begins after the safety follow-up visit and continues until death or full consent withdrawal. Efficacy assessments including radiographic assessments, cystoscopy and urine cytology will continue to be performed until recurrence by BICR (local/regional invasive or metastatic) or metastatic recurrence by investigator assessment, whichever comes later. Subjects who develop recurrence by BICR (local/regional invasive or metastatic) or metastatic recurrence by investigator assessment prior to the long-term follow-up phase will not be followed for disease status during the long-term follow-up phase. After that time, subjects will be followed for survival every 6 months for 1 year, then annually thereafter (via telephone or office visit) for 1 year after the time when the final DFS event goal is reached (ie, EOS).

Overall Survival Time (OS)

Overall survival time is calculated as the number of months from randomization to death (date of death - date of randomization + 1)/(365.25/12). Subjects who have not died (no record of death) or are lost to follow up will be censored at the date of last known to be alive. Subjects who

withdraw consent for study participation, including consent to be followed, will be censored on the date of withdrawal.

Metastasis-free Survival Time (MFS)

The investigator reviewed MFS is defined as the time from randomization to any metastatic recurrence as determined by the investigator or death due to any cause, whichever occurs earlier. Subjects without documented metastatic recurrence and are still alive, will be censored at the last radiology assessment, or at the time of randomization if no radiology disease assessments are performed after the baseline visit.

Disease-free Survival Time (DFS)

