Disease-free survival time is calculated as the number of months from randomization to the date of local/regional invasive or metastatic recurrence or death due to any cause (referred as DFS event) ((date of DFS event - date of randomization + 1)/ (365.25/12)). Subjects without recurrence (local/regional invasive or metastatic) or death will be censored at the last radiology assessment if previous cystoscopy result within 6 months is negative for muscle invasive disease, otherwise, DFS will be censored at the last complete recurrence assessment. Subjects who have no disease assessments after baseline will be censored on the randomization date. The primary DFS endpoint will be based on the central review (BICR), while for the secondary endpoint, the investigator reviewed DFS will be based on investigator review.

DFS including intraluminal low risk recurrence

The investigator reviewed DFS including intraluminal low risk recurrence is defined as the time from randomization to any recurrence as determined by investigator, or death due to any cause, whichever occurs earlier. For subjects without documented recurrence and are still alive, they will be censored at the last complete disease assessment (or, if no disease assessments are performed after the baseline visit or no death has been recorded, at the time of randomization).

Relative dose intensity

The relative dose intensity is defined as cumulative actual dose a subject have received divided by the planned cumulative dose. For example, a subject takes study drug from Day 1 to Day 21 at 125 mg/day; then from Day 29 to Day 30 at 100 mg/day, and end treatment afterward. The cumulative actual dose $=(21*125)+(100*2)=2825$ mg; the planned cumulative dose $=(21*125)+(125*2)=2875$ mg. The relative dose intensity $= 2825/2875=98.3\%$.

Study Day 1

Study Day 1 is defined as the day of the first administration of study treatment after randomization.

Treatment Duration

Treatment duration is defined as last dose date – first dose date +1.

On Treatment Period

On treatment period is defined as first administration of study treatment through 30 days after the last administration of study treatment inclusively.

Treatment-emergent Adverse Event

A treatment-emergent adverse event is defined as an adverse event that occurs on or after the first administration of study treatment and within 30 days after the last administration of study treatment.

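### Censoring at randomization is joined by 'or' where 'and' is needed in the protocol's DFS and MFS rules, and the SAP's primary DFS sentence still makes no exception for a death before any assessment

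*Protocol*

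**What the plan says.** **Protocol 11.3.3, primary DFS.** Death is an event: the endpoint runs to recurrence "or death due to any cause, whichever occurs earlier". Living, recurrence-free subjects are censored at an assessment date. For those with a bladder, "DFS will be censored at the last radiology assessment if the previous cystoscopy result within 6 months is negative for muscle invasive disease", and otherwise at the last complete recurrence assessment. The paragraph then ends: "Subjects who have no disease assessments after baseline or no death recorded will be censored on the randomization date".

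**Protocol 11.3.3, secondary endpoints.** Both clauses are parentheses inside a sentence about subjects who are still alive.
- DFS including intraluminal recurrence: "if no complete disease assessments are performed after the baseline visit or no death recorded, at the time of randomization day".
- MFS: "if no radiology assessments are performed after the baseline visit or no death recorded, at the time of randomization day".

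**SAP section 6.**
- Primary and investigator DFS, with the death clause gone: "Subjects who have no disease assessments after baseline will be censored on the randomization date".
- MFS, confined to living subjects, with the death clause gone: "or at the time of randomization if no radiology disease assessments are performed after the baseline visit".
- DFS including intraluminal recurrence, confined to living subjects, with the death clause kept: "if no disease assessments are performed after the baseline visit or no death has been recorded, at the time of randomization".

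Neither document anywhere limits censoring at randomization to subjects with neither an assessment nor a death.

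**The concern.** A rule that sends a subject to the randomization date should apply only when nothing is known after randomization. With 'or', either missing fact is enough. In the primary DFS rule this has two effects. A death before the first assessment becomes a censoring at time zero. Every living, event-free subject also satisfies the second condition and loses all follow-up.

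The second effect is so gross that a programmer would notice it. The first is less visible, because it touches few subjects and the SAP's primary and investigator DFS sentence, taken alone, asks for the same thing. The affected group can exist. The first scheduled post-baseline scan is at Cycle 4 Day 1, after three 28-day cycles (3 x 28 = 84 days, 12 weeks), and the ITT population includes every randomized subject, treated or not.

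**Working it through.** **1. The plan's own figures.** No figure is attached to the censoring rule, so the design was reproduced first. Inputs from Protocol 11.2: HR 0.5, one-sided 0.025, about 80% power, 46% placebo recurrence by 2 years and then 5% per year, 3-year accrual, 1-year follow-up, 10% yearly drop-out.
- Freedman: events = (1.960 + 0.842)^2 x ((1 + 0.5)/(1 - 0.5))^2 = 7.85 x 9, or 71. Power at 70 events = Phi(sqrt(70)/3 - 1.960) = 79.6%.
- Schoenfeld: 66 events. Power at 70 events is 82.6%, or 80.6% once the interim futility boundary is applied.
- Expected events at 4 years for N = 218, with placebo hazards -ln(0.54)/2 = 0.308 and then -ln(0.95) = 0.051 per year: 69.7 to 70.1.

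The 218 subjects, 70 events and 80% power reproduce. None of them depends on the censoring sentence.

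**2. The primary DFS rule, case by case.**

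| Subject | Protocol, 'or' as written | With 'and' | SAP primary/investigator DFS as written |
|---|---|---|---|
| Assessed, died | event | event | event |
| Assessed, alive, event-free | day 0 | last assessment | last assessment |
| Assessed, alive, recurrence | day 0 if the sentence is read alone | event | event |
| Not assessed, died | day 0 | event at death | day 0 if the sentence is read alone |
| Not assessed, alive | day 0 | day 0 | day 0 |

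Only the 'and' column agrees with both the endpoint definition and the last-assessment sentences.

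**3. The six clauses side by side.**
- Protocol primary DFS: 'or', not confined to living subjects. It can lose unassessed deaths and event-free follow-up.
- Protocol DFS including intraluminal recurrence, protocol MFS, and SAP DFS including intraluminal recurrence: 'or', living subjects only. The absence of a death is then always true, so event-free follow-up is lost, but a dead subject never reaches the clause.
- SAP primary and investigator DFS: no 'or', but no death exception. An unassessed death can be lost.
- SAP MFS: no 'or', living subjects only. Correct as it stands.

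**4. Size.**
- Event-free subjects under the literal protocol rule at the planned analysis: 218 - 70 = 148 (148/218 = 68%).
- Deaths before any assessment: not given. At an assumed 1% to 3% of 218, this is 2.18 to 6.54, so 2 to 7 subjects.
- Effect on a Kaplan-Meier curve: with n at risk in an arm, one early death lowers the curve by 1/n. Censored at day 0, it lowers it by nothing. At the planned 218/2 = 109 per arm that is 1/109 = 0.9 percentage points per death. With fewer randomized it is more; the documents do not give the final number.

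**5. Whether the literal rule could work at all.** Simulation used the design inputs above, 4,000 trials per scenario, an unstratified log-rank test and no futility stop. Assumptions not in the documents: 5-20% of DFS events are deaths without recurrence, post-recurrence death hazard 0.3-1.0 per year, and 0-5% of subjects have no post-baseline assessment. The 'or' runs apply the sentence on its own, so living subjects with a recurrence also go to day 0.
- 'And': 68-70 events, power 79-81%, HR 0.50-0.51.
- Literal 'or': 26-51 events, 77-88% of subjects at day 0, 88-94% of follow-up lost, HR 0.92-0.94, power 4-5%.

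This shows that the sentence cannot be applied as written. It does not predict what would be programmed.

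**The case against.** The strongest reply is that the intent is plain. The protocol paragraph makes death an event, limits the preceding censoring sentences to living, recurrence-free subjects, and then evidently means subjects with neither an assessment nor a death. The SAP paragraph can be read the same way: events are defined first and the censoring sentences follow, so a death would already have been counted. Protocol 11.1 also leaves missing-data handling to the SAP, and the SAP has removed the faulty clause for primary and investigator DFS and for MFS.

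Much of this stands, and it rules out several stronger readings that a reader might infer:
- *That all the SAP's Kaplan-Meier curves rest on the 'or'.* Only DFS including intraluminal recurrence keeps it.
- *That deaths are discarded for every endpoint.* The MFS and intraluminal clauses apply to living subjects only.
- *That 148 subjects, or 2-7 deaths out of 70 events (3-10%), will be lost.* Those figures belong to an analysis that early termination cancelled. SAP sections 1, 5 and 8.1 say that the required events were not reached and that nothing will be tested.
- *That the error will pass unnoticed into the results.* The derivation program is not in the documents, so this cannot be established either way.

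One part of the reply fails. The SAP does not state the intended rule. Its primary and investigator DFS sentence names only the missing assessment as the condition and leaves the unassessed death to inference. Swapping 'or' for 'and' does not reach that sentence, because it contains no 'or'.

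**Conclusion.** The point holds in limited form. The protocol's primary DFS censoring sentence is wrong as written, because it contradicts both the endpoint definition and the sentences before it. Three further clauses (protocol MFS, protocol DFS including intraluminal recurrence, SAP DFS including intraluminal recurrence) carry the same fault for event-free follow-up only. For the planned analysis the sentence that matters is the SAP's primary and investigator DFS rule, which lacks a death exception.

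The effect is confined to descriptive Kaplan-Meier curves; sample size, alpha and boundaries are untouched. Its size depends on how many subjects died without a post-baseline assessment. The documents do not say; 2-7 rests on an assumed 1-3% of the planned 218 and could be zero in the subjects actually randomized. This is a drafting error whose meaning can be recovered, but it is worth correcting because a small dataset makes each early death count for more.

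**What to change.** - **SAP section 6, primary and investigator DFS (most important).** Write: 'Subjects who have no disease assessments after baseline and no recorded death will be censored on the randomization date; a death without prior assessment is an event on the date of death.'
- **SAP section 6, DFS including intraluminal recurrence.** Change 'or' to 'and' in the censoring clause.
- **Protocol 11.3.3, primary DFS, DFS including intraluminal recurrence, and MFS.** Change 'or' to 'and' in the three sentences. If no amendment will be issued for a closed study, a clarification in the SAP would serve the planned analysis.
- **Derivation program.** Check that any randomized subject who died without a post-baseline assessment is an event on the date of death, and that living, event-free subjects with assessments are censored at the last qualifying assessment.

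The cost is one word in each of four places, one rewritten SAP sentence and one program check. No design parameter changes.

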11.3.4 Pharmacokinetic Analyses

C_{trough} and C_{max} will be estimated from the PK concentration data collected (Section 10.2). PK concentration will be summarized as appropriate. Data may be used for population PK analysis and PK/PD analysis and results may be reported separately.

11.3.5 Biomarker Analyses

Summary statistics for genetic alterations among different groups of all prescreened subjects will be provided.

Biomarker analysis will be performed using available tumor samples in order to detect changes from baseline in the genetic profiles in tumor samples from treated subjects. The difference in biomarker results from samples taken before and during treatment may be explored.

In addition, correlation between genetic biomarkers, subject demographics, and clinical endpoints may also be explored. The SAP will provide more details of such descriptive analyses.

11.3.6 Analyses of Quality of Life Assessments

QOL assessments (EQ-5D-5L and EORTC QLQ-C30) will be analyzed using a random effects mixed model controlling for baseline scores and stratification factors to assess the difference in treatment arms. Two-sided 95% CI will be calculated for the difference between the 2 treatment arms.

In addition, descriptive summaries on the observed data (including change from baseline) will be summarized at each assessed time point. Compliance with QOL assessments will be reported.

11.3.7 Interim Analysis

One formal interim analysis of DFS will be performed when approximately 35 confirmed DFS events by BICR (independent of investigator assessment) have occurred. A Haybittle-Peto boundary will be used for the efficacy boundary with a fixed one-sided alpha of 0.00005 spent at the interim analysis for centrally reviewed DFS, and the rest of the alpha (one-sided alpha 0.025) spent at the primary DFS analysis. A Lan DeMets spending function approximating O'Brien-Fleming boundaries will be used for the non-binding futility boundary.

At the interim analyses, the study will not be stopped for efficacy if the efficacy boundary for DFS is crossed.

The study may be stopped due to futility at the interim DFS analysis if the futility boundary for testing DFS is crossed. The futility stopping boundary is non-binding to allow for additional considerations.

If a sample size increase is deemed necessary based on the interim result using the promising zone approach, the sample size/event goal will be increased by a maximum of 50% (328/105). The details of the sample size adaptation method based on interim analysis will be prespecified in the adaptation plan.

11.3.8 Safety Analyses

Safety analyses will be performed for all subjects who receive ≥ 1 dose of study drug according to the treatment they received.

11.3.8.1 Treatment Exposure

Duration of treatment will be summarized by treatment arm. In addition, the cumulative dose and the relative dose intensity (cumulative actual dose/planned cumulative dose) will be summarized. The number of subjects with dose interruptions or dose reductions will be tabulated by treatment arm.

11.3.8.2 *Adverse Events*

Study data will be monitored on an ongoing basis by the clinical study team to ensure subjects' safety. Additional safety reviews will be performed by the DMC periodically throughout the study. These reviews will include all available data on incidence of AEs, SAEs including deaths, and events leading to treatment discontinuation.

All reported AEs will be assigned to a system organ class and preferred term according to the Medical Dictionary for Regulatory Activities (MedDRA).

AEs will be considered to be treatment-emergent if the event occurs on or after the first administration of study drug and within last dose date +30 days. The subject incidence rates of treatment-emergent AEs will be tabulated by system organ class, preferred term and severity grade for all serious, treatment related, and serious treatment related treatment-emergent AEs. Each of these outputs will include tabulation by maximum severity for each system organ class and preferred term as reported by the investigator based on CTCAE, version 5.0. Summary tables also will be provided for treatment-emergent AEs leading to study drug modification (discontinuation, hold, or reduction). All "on treatment" deaths (ie, deaths that occur after the first administration of study drug and within 30 days after last dose of study drug) will be summarized. Listings and/or narratives of "on-treatment" deaths, SAEs, and AEs leading to study treatment modification (discontinuation, hold, or reduction), will also be provided.

The summaries of the subject incidence rates of treatment-emergent AEs by system organ class and preferred term reported AEs will also be provided for subgroups defined by age, sex, and race (if feasible).

11.3.8.3 *Other Safety Findings*

Laboratory parameters for hematology and serum blood chemistry will be summarized at baseline, at each visit or selected visits, for the maximum and minimum observed postbaseline values, and the last observed value, along with the change from baseline. Tables of shifts in severity (by CTCAE version 5.0) from baseline for selected laboratory parameters also may be provided. Graphical representations of aggregate data may also be presented for parameters of interests.

Vital signs, physical examination results, ophthalmic assessment, and ECG results will be summarized by treatment arm using descriptive statistics (including changes from baseline, if appropriate).

12 DATA COLLECTION AND MANAGEMENT

12.1 Data Confidentiality

All records identifying the subject will be kept confidential and, in accordance with the applicable laws and/or regulations, will not be made publicly available.

Subject names will not be supplied to the sponsor. Only the subject number will be recorded on the eCRF. If the subject name appears on any other document or trial materials, then that information must be redacted before a copy of the document is supplied to the sponsor. Trial data

stored on a computer will be stored in accordance with local data protection laws and regulations. Subjects will be informed in writing that representatives of the sponsor, IRB/IEC/Research Ethics Board (IRB/IEC/REB), or regulatory authorities may inspect their medical records to verify the information collected, and that all personal information made available for inspection will be handled in strictest confidence and in accordance with local data protection laws and regulations.

If the results of the trial are published, the subjects' identity will remain confidential.

The investigator will maintain a list to enable subjects' records to be identified in accordance with applicable laws and regulations.

The data collection system for this study uses built-in security features to encrypt all data for transmission in both directions, preventing unauthorized access to confidential participant information. Access to the system will be controlled by a sequence of individually assigned user identification codes and passwords, made available only to authorized personnel who have completed prerequisite training.

Either year of birth or exact date of birth (depending on local privacy regulations) will be recorded to establish that the subject satisfies protocol age requirements and to enable appropriate age-related normal ranges to be used in assessing laboratory test results.

